10.2.2 Ionising Radiation Exposure

Radiation dosimetry studies were conducted in order to estimate the radiation exposure following the administration of [11C]PBR28. The dosimetry of [11C]PBR28 was estimated in 7 human volunteers (4 male, 3 female) (Brown et al., 2007). Based on these data, the effective dose (ED) of [11C]PBR28 was estimated at 0.0066 mSv/MBq. Each volunteer will receive a maximum dose of 300 MBq of [11C]PBR28in each of their PET scans. The doses administered are adjusted to deliver the minimal radiation exposure compatible with a good quality PET signal. In addition, a low-dose CT scan of the head will be acquired to estimate attenuation correction prior to each PET scan. The radiation exposure due to the 2 scans with [11C]PBR28 will be 3.96 mSv, and 0.72 mSv from the 2 low-dose CT scans, yielding 4.68 mSv in total for the study. This exposure will place the study in category IIb of the International Commission on Radiological Protection (ICRP), an international workgroup on radiological protection.

10.2.3 Intravenous cannulae

Venous blood will be collected at screening to determine TSPO genotype and for routine safety tests. In addition a venous cannula will be inserted into a forearm or cubital vein for radiotracer administration and blood collection for pharmacokinetic analysis. Insertion of cannulae may lead to some transient pain and discomfort, and some bruising at the cannulation site.

10.2.4 PET

PET scans will be conducted according to GCP and GMP compliant procedures at the Imanova facility. Subjects will be screened for contraindications to PET scanning as per standard Imanova procedures. Before the start of each PET scan a venous cannula will be inserted into a forearm or cubital vein, for the administration of [11C]PBR28, and the subject will be positioned comfortably within the PET-CT scanner. A short low-dose CT of the brain will be conducted, and following this the PET emission data will be collected for approximately 90 minutes starting with the intravenous injection of [11C]PBR28. The primary discomfort arises from the need for subjects to lie supine during the scan. The scan will be stopped or abandoned if the subject is unable to complete the scan.

10.2.5 MRI

As a standard procedure, MR images will be evaluated by a radiologist. In the unlikely event of an unexpected and clinical significant finding on structural MRI which may require further investigation, participants and/or their General Practitioner will be informed, with the participant's consent. There are no known risks to subjects associated with MRI scanning, provided subjects have no contraindications to MRI as listed in the exclusion criteria. Some participants may find the PET and MRI scanning environments claustrophobic. Participants with severe anxiety in confined spaces will be excluded from the study. Furthermore, potential risks associated with metallic implants injury will be eliminated by screening during study enrolment and prior to the scan.

10.2. Clinical Assessments

After providing informed consent, the medical history will be documented in a CRF. Patients will also undergo a neurological examination. On the day of the PET and MRI examinations, the patients will be asked for the any events in the interim period since the screening examination. They will undergo a physical examination with a focus on neurological findings. Specifically, they will be assessed using the following tools: **mRS:** The mRS measures independence, rather than neurological function, with specific tasks pre- and post stroke ¹⁴⁻¹⁷. The scale consists of 7 grades, from 0 to 6, with 0 corresponding to no symptoms and 6 corresponding to death. The premorbid mRS will be scored through interviews with the participant and/or family caregiver. Raters will be required to be certified in the use of the mRS. The mRS will be completed by a telephone interview for any subjects who fail to attend their Day 90 Follow-Up or Early Termination visit. The mRS takes less than 5 minutes to administer.

BI: The BI consists of 10 items that measure a person's daily functioning, specifically the activities of daily living and mobility ¹⁸⁻²⁰. The items include feeding, moving from wheelchair to bed and returning, grooming, transferring to and from a toilet, bathing, walking on a level surface, going up and down stairs, dressing, and maintaining continence of bowels and bladder. The assessment can be used to determine a baseline level of functioning and can be used to monitor change in activities of daily living over time. The items are weighted according to a scheme developed by the authors. The person receives a score based on whether they have received help while doing the task. The scores for each of the items are summed to create a total score up to a maximum of 100. The higher the score, the more "independent" the person is. The BI takes less than 5 minutes to administer.

NIHSS: The NIHSS is a reliable tool for rapidly evaluating the effects of acute cerebral infarction ²¹. Raters will be required to be certified in the use of the NIHSS. A trained observer rates the subject's ability to answer questions and perform activities relating to level of consciousness, language, visual-field loss, extraocular movement, motor strength, ataxia, dysarthria, sensory loss, and extinction and inattention (formerly neglect). There are 15 items. Ratings for each item are scored with 3 to 5 grades, with 0 as normal and a maximum possible total severity score of 42 for all items. There is an allowance for untestable items. The test takes approximately 10 minutes to complete.

MoCA: The Montreal Cognitive Assessment (MoCA) is designed as a rapid screening instrument for mild cognitive dysfunction. It assesses different cognitive domains: attention and concentration, executive functions, memory, language, visuoconstructional skills, conceptual thinking, calculations, and orientation. Time to administer the MoCA is approximately 10 minutes. The total possible score is 30 points. A score of 26 or above is considered normal.

Beck's Depression Inventory: The Beck Depression Inventory Second Edition (BDI-II) is a 21-item self-report instrument intended to assess the existence and severity of symptoms of depression. Each of the 21 items corresponding to a symptom of depression is summed to give a single score for the BDI. There is a four-point scale for each item ranging from 0 to 3. On two items (16 and 18) there are seven options to indicate either an increase or decrease of appetite and sleep. Cut score guidelines for the BDI are given with the recommendation that thresholds be adjusted based on the characteristics of the sample, and the purpose for use of the BDI. Total score of 0-13 is considered minimal range, 14-19 is mild, 20-28 is moderate, and 29-63 is severe.

Venous Blood Samples

Genetic Testing: At the screening visit, participants will have a blood sample of up to 15mls taken which will processed at Hammersmith Hospital for TSPO Polymorphism genotyping. The results will confirm whether the participants meet the full eligibility criteria of the trial. If the results show genetic polymorphism consistent with low TSPO binding affinity (expected in 10% of the population) those participants will be considered screen fails and will not be included in the trial. The test is purely to determine eligibility, the samples will be destroyed in accordance with local guidelines after testing is complete. Haematology and Chemistry: Participants will have a full blood count, renal and kidney function tests at screening if they have not had recent testing done as part of clinical care. It is expected that most participants will not require this.

Systemic Inflammatory Markers: To assess systemic inflammatory markers, venous blood samples of 15ml will be takenon both days of the PET und MRI examinations. Blood will be rapidly frozen and stored in -80 specimen freezers at Imperial College London. Cytokines in blood will be measured using Multiplex ELISA. Samples will be processed on site at Imperial College London and any remaining samples will be stored for future use by the research team but will not be transferred out of Imperial College London.

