- To characterize post-stroke TSPO glial expression in relation to measures of stroke severity (infarct size, volume and location; NIHSS) and functional outcome (mRS,BI, depression scale, MoCA)
- To characterize post-stroke TSPO glial expression in relation to systemic inflammatory markers in blood

The endpoints that relate to these objectives are:

- PET-derived measures of TSPO radiotracer uptake in the infarct and peri-infarct areas at day 15 and day 90 after a stroke
- PET-derived measures of TSPO radiotracer uptake in ROIs distant from the infarct area (e.g. thalamus, hippocampi, amygdalae and midbrain) at day 15 and day 90 after a stroke
- Correlation of PET-derived measures with clinical and imaging measures of stroke severity (stroke volume, size and NIHSS) and functional outcome (mRS Barthel index, MoCA, depression,) at day 15 and day 90
- Correlation of infarct volume and MRI measures of white matter tract injury determined from DTI MRI with measures of thalamic TSPO uptake (timeactivity curve; measures of mean and max TSPO uptake on summed image sets from TSPO PET
- Correlation of PET derived measures with inflammatory markers in the blood (e.g. cytokines)

Study Design: This is an exploratory, prospective, natural history, imaging

cohort study.

Study Location and Number

of Sites:

The recruiting site will be Imperial College Healthcare NHS

Trust. All study scans will be performed by Imanova,

Hammersmith Hospital

Number of Planned Subjects: Between 15 and 25 subjects, with recruitment ending when

15 participants have completed all study procedures.

Study Population: Subjects aged 18-85 with a supratentorial ischemic stroke of

moderate severity as measured by NIHSS >4 and evidence

of infarction on clinical brain scan at time of stroke:

Duration of Treatment and

Follow-up:

Subjects will participate in this study for approximately 90

days. No treatment will be started as part of the trial

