6. STUDY OBJECTIVES AND ENDPOINTS

6.1. Objectives and Endpoints

The objectives of this study are:

- To characterize TSPO glial expression in specific regions of interest defined on correlative brain MRI (ROIs; infarct, peri-infarct, thalamus) in the subacute (day 15+3) and chronic (day 90+7) phases after an ischemic stroke;
- To determine the magnitude and variability of TSPO uptake at these ROIs during the assessment period;
- To describe changes in TSPO expression between 15 and 90 days
- To explore the relationship between TSPO uptake, blood and infarct volume, and measures of Wallerian degeneration; and,
- To characterize post-stroke TSPO glial expression in relation to measures of stroke severity (infarct size, volume and location; NIHSS) and functional outcome (mRS, BI, MoCA, Beck depression inventory)
- To characterize post-stroke TSPO glial expression in relation to systemic inflammation in blood

Endpoints that correlate to these objectives are:

- PET-derived measures of TSPO radiotracer uptake in the infarct and peri-infarct areas at day 15 and day 90 after a stroke;
- PET-derived measures of TSPO radiotracer uptake in ROIs distinct from the infarct area (e.g., thalamus, hippocampi, amygdalae and midbrain) at day 15 and day 90 after a stroke:
- Correlation of PET-derived measures with clinical and imaging measures of stroke severity (stroke volume, size and NIHSS) and functional outcome (mRS and BI) at day 15 and day 90
- Correlation of infarct volume and MRI measures of white matter tract injury determined from DTI MRI with measures of thalamic TSPO uptake (time-activity curve; measures of mean and max TSPO uptake on summed image sets from TSPO PET.
- Correlation of PET derived measures with inflammatory markers in the blood (e.g. cytokines)

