12.2. Analysis Population

All eligible subjects who have completed at least one PET-MRI scan will be included in the analysis

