12.4. Endpoints Analysis

PET-derived measures including SUVR in the infarct and peri-infarct area, and ROIs distant from the infarct area at Day 15 and Day 90 will be summarized by visit. Various aspects of change over time including magnitude, variability and pattern will be assessed. The relationship between PET-derived measures and stroke severity (including stroke volume, size, NIHSS) will be examined using methods including linear correlation and regression. Also, the relationship between PET-derived measures and functional outcomes , markers of systemic inflammation and relationship between measures of white matter tract injury and measures of thalamic uptake will be explored.

A detailed statistical analysis plan will be established before the beginning of the analysis.

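### A missed Day 90 visit triggers a telephone mRS but no Barthel index, so Day 90 BI is lost where mRS is kept; same-visit PET correlations are not affected

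*Combined protocol and SAP*

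**What the plan says.** Section 10.2 (Clinical Assessments) provides a fallback for one scale only: "The mRS will be completed by a telephone interview for any subjects who fail to attend their Day 90 Follow-Up or Early Termination visit". The BI paragraph that follows gives no telephone or proxy route, and no other section supplies one. It does say that "The BI takes less than 5 minutes to administer".

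The endpoint list in section 6.1 names the two scales together: "functional outcome (mRS and BI) at day 15 and day 90". The synopsis endpoint and the 6.1 objective also list MoCA and depression.

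On scoring, the mRS runs from 0 to 6, "with 0 corresponding to no symptoms and 6 corresponding to death". For the BI, "The scores for each of the items are summed to create a total score up to a maximum of 100", with no value for death.

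Section 12.2 sets the population: "All eligible subjects who have completed at least one PET-MRI scan will be included in the analysis". A patient scanned only at Day 15 therefore stays in. Section 12.4 says that "the relationship between PET-derived measures and functional outcomes" will be explored. It does not say which PET visit goes with which outcome visit, and it defers detail to a later SAP.

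Section 9.2 requires withdrawal of subjects who are unwilling or unable to comply. It bars any new data after loss of capacity.

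**The concern.** The plan treats Day 90 function as worth recovering by telephone when the visit is missed, but recovers it on one of two scales that the endpoint list names together. The BI asks about daily activities and is short, so nothing in the text explains leaving it off the call.

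The visit involves about 90 minutes of PET (section 10.2.4) and up to 90 minutes of MRI (section 10.1.2). It is plausible, though the documents do not say so, that more disabled patients miss it more often. The BI would then lose part of its low end while the mRS kept it. If Day 15 uptake appeared to relate more strongly to Day 90 mRS than to Day 90 BI, part of that contrast could come from who was measured and not from the scales. A later SAP can set analysis rules, but it cannot recover a BI that was never collected.

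**Working it through.** The plan has no figure to reproduce. Section 12.1 sets the sample size on feasibility and states no power, effect size or dropout rate.

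**Step 1. Where the two scales can differ**

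| Analysis | Patient who misses Day 90 | mRS and BI on different patients? |
|---|---|---|
| Day 15 PET vs Day 15 function | both scales already scored in person | No |
| Day 90 PET vs Day 90 function | no Day 90 PET, so out for both scales | No |
| Day 90 functional summaries | mRS by telephone, BI missing | Yes |
| Day 15 PET vs Day 90 function | mRS by telephone, BI missing | Yes |

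Section 12.4 neither specifies nor excludes the last pairing.

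**Step 2. Ceiling on the number affected**

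The synopsis plans "Between 15 and 25 subjects, with recruitment ending when" 15 have completed all procedures. The most who could have a Day 90 mRS without a BI is N − 15:

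- N = 18: 3 of 18 (17%)
- N = 20: 5 of 20 (25%)
- N = 25: 10 of 25 (40%)

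This is not an estimate of non-attendance. Subjects count as enrolled at consent (section 9.1), so the excess over 15 also holds genotype screen failures (expected in 10%, or 0.10 × 25 = 2.5 of 25), patients never scanned, and withdrawals.

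**Step 3. Possible effect on the correlation**

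All inputs here are assumptions, not document figures: 20 patients with a Day 15 scan, uptake and outcome bivariate normal, true correlation 0.6 in size, k = 2 to 5 patients without a BI, 10,000 simulated cohorts per setting. The result is the mean Pearson correlation among those left.

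| Who is lost | k = 2 | k = 3 | k = 4 | k = 5 |
|---|---|---|---|---|
| None (all 20) | 0.59 | 0.59 | 0.59 | 0.59 |
| Loss tracks outcome plus noise of equal variance | 0.56 | 0.55 | 0.54 | 0.54 |
| The k worst outcomes | 0.53 | 0.51 | 0.49 | 0.47 |

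Random loss leaves the mean essentially unchanged (0.58 to 0.59), so the fall comes from selection and not from the smaller number. With a true correlation of 0.4, the mean falls from 0.39 to 0.37-0.35 (partial selection) or 0.34-0.30 (worst case).

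**Step 4. Comparison with sampling error**

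The Fisher 95% interval is tanh(atanh(r) ± 1.96/√(n − 3)). For r = 0.59 and n = 20, atanh(0.59) = 0.678 and 1.96/√17 = 0.475, giving 0.20 to 0.82. A shift of 0.03 to 0.05 (partial selection) or 0.06 to 0.12 (worst case) is small beside that width, though it is a bias in one direction.

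**The case against.** The strongest reply is about scope. The natural reading of the 6.1 endpoint pairs PET and function at the same visit, and there the telephone rule creates no mismatch at all. A reader might infer that the functional correlations as a whole rest on different patients for mRS and BI. The documents do not support that, and this objection stands in full. What survives is the Day 90 summaries and the Day 15 to Day 90 pairing, which section 12.4 leaves open.

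A reader might also take the missing BI value for death as an omission in the plan. It is not: the BI has no grade for death by construction. It needs only a stated handling rule in the SAP.

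NIHSS, MoCA and the Beck inventory have no telephone rule either, so adding the BI does not put every outcome on the same patients. That is true. The case for the BI is that it sits beside the mRS in the endpoint, is short, and asks about daily activities that can be covered on the same call.

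Some disabled non-attenders may be withdrawn under section 9.2, which shrinks the group by an unknown amount. That also stands. Finally, the study is exploratory and descriptive, with a SAP still to come. This limits the stakes, but does not remove a gap in data collection.

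**Conclusion.** The gap is real and narrow. Among patients with a Day 15 scan who miss Day 90 and are neither withdrawn nor without capacity, Day 90 mRS is kept and Day 90 BI is lost. It touches the Day 90 functional summaries and any analysis of Day 15 uptake against Day 90 function, and nothing else.

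The number affected cannot be read from the documents. Reading 40% as the expected loss would be wrong: 10 of 25 is a ceiling made up of several kinds of loss, and the affected group should be well below it. The simulated attenuation rests on assumed values for the cohort size, true correlation, number lost and link between attendance and outcome. The worst-case row needs every one of the poorest outcomes to be a non-attender. No powered test is at risk. This is a modest, low-cost improvement to description and precision.

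**What to change.** **Protocol, section 10.2.** In the telephone sentence, make the subject the mRS and the BI. Leave the rest as it stands, including its reference to the Early Termination visit. Record for each score whether it was taken by telephone or in person.

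**SAP.** For Day 15 uptake against Day 90 function:
- analyse mRS and BI on the same survivors;
- report the number of deaths and the n behind each correlation;
- add a rank-based sensitivity analysis with death as the worst outcome on both scales.

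State which PET visit is paired with which outcome visit. Leave the section 12.2 population unchanged, so that a patient with only a Day 90 scan is still included.

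**Cost.** Under 5 more minutes on a call already required, a short protocol edit and a few SAP sentences. The drawback is a mix of telephone and in-person BI, which the plan already accepts for the mRS; recording the mode lets it be examined.

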11. SAFETY DEFINITIONS, MONITORING, AND REPORTING

Throughout the course of the study, every effort must be made to remain alert to possible adverse events (AEs). If an AE occurs, the first concern should be for the safety of the subject. If necessary, appropriate medical intervention will be provided. At the signing of the ICF, each subject or his/her legally authorized representative and/or main caregiver must be given the names and telephone numbers of study site staff for reporting AEs and medical emergencies.

11.1. Definitions

11.1.1. Adverse Event (AE)

The present study is observational. No drugs will be given as a therapeutic intervention.

Therefore, only adverse reactions related to study procedures including PET and MRI scanning, blood sampling and clinical examination will be recorded.

11.1.2. Serious Adverse Event

An SAE is any untoward medical occurrence that

- results in death
- in the view of the Investigator, places the subject at immediate risk of death (a life-threatening event); however, this does not include an event that, had it occurred in a more severe form, might have caused death
- requires inpatient hospitalization or prolongation of existing hospitalization
- results in persistent or significant disability/incapacity, or
- results in a congenital anomaly/birth defect.

An SAE may also be any other medically important event that, in the opinion of the Investigator, may jeopardize the subject or may require intervention to prevent one of the other outcomes listed in the definition above. (Examples of such medical events include allergic bronchospasm requiring intensive treatment in an emergency room or convulsions occurring at home that do not require an inpatient hospitalization.)

11.1.3. Prescheduled or Elective Procedures or Routinely Scheduled Treatments

A prescheduled or elective procedure or a routinely scheduled treatment will not be considered an SAE, even if the subject is hospitalized; the study site must document all of the following:

- The prescheduled or elective procedure or routinely scheduled treatment was scheduled (or was on a waiting list to be scheduled) prior to obtaining the subject's consent to participate in the study.
- The condition requiring the prescheduled or elective procedure or routinely scheduled treatment was present before and did not worsen or progress in the opinion of the

Investigator between the subject's consent to participate in the study and the time of the procedure or treatment.

• The prescheduled or elective procedure or routinely scheduled treatment is the sole reason for the intervention or hospital admission.

If a subject is hospitalized due to local requirements for administration of standard of care, the hospitalization should not be considered an SAE unless one of the requirements in Section 11.1.2 is met.

11.2. Safety Classifications

11.2.1. Investigator Assessment of Events

All events must be assessed to determine the following:

- If the event meets the criteria of an SAE as defined in Section 11.1.2
- The relationship of the event to study intervention as defined in Section 11.2.1
- The severity of the event as defined in Section 11.2.2

